#### **2.4 Rationale for Dose and Schedule of Administration**

The Phase 1 program evaluated ISIS 681257 doses of 10 mg, 20 mg, and 40 mg given weekly that were found to be generally well-tolerated and to induce clinically-relevant reductions in Lp(a).

The range of dosing proposed for the present study will provide the equivalent drug exposure of 5 mg, 10 mg, 15 mg, and 20 mg administered weekly, and is predicted (based on modelling of PK/PD data obtained in Phase 1 study) to result in mean reductions from baseline in plasma Lp(a) ranging from approximately 60% to 85% at steady-state.

The highest dose selected for this study, 20 mg per week, is predicted to provide an approximately 85% reduction in Lp(a) at steady-state that is expected to be sufficient to bring almost all patients with hyperlipoproteinemia(a) into the normal range ( $Lp(a) \leq 30$  mg/dL).

The present study will also evaluate safety and efficacy at different dosing frequencies: every 4 weeks, every 2 weeks, and weekly. Patients with hyperlipoproteinemia(a) will require chronic treatment and thus every 2 weeks or every 4 weeks dosing regimens, if safe and well-tolerated, may provide advantages over weekly dosing in terms of convenience and compliance for patients. Dosing regimens of 20 mg every 2 weeks and 40 mg every 4 weeks will test if similar monthly exposure, at different frequencies of administration, will achieve similar safety and similar level of Lp(a) reduction since the reduction achieved by a given dose level is principally

driven by total exposure, while individual dose levels and the related peak concentration ( $C_{\max}$ ) may influence tolerance and safety.

### 3. EXPERIMENTAL PLAN

#### 3.1 Study Design

This is a Phase 2, multicenter, randomized, double-blind, placebo-controlled, dose-ranging study. Approximately 270 patients will be randomized in a 5:1 ratio (225 ISIS 681257 and 45 placebo) to receive ISIS 681257 or placebo. Study Drug (ISIS 681257 or placebo) will be administered SC every week, every 2 weeks (biweekly), or every 4 weeks, depending on cohort assignment, for up to 52 weekly doses, up to 26 every 2-week doses, or up to 13 every-4-week doses.

The primary analysis time point is at Week 25 for patients who received every 4-week dosing (Cohorts A-C) and at Week 27 for patients who received 2-week or weekly dosing (Cohorts D and E). For patients continuing treatment beyond the primary analysis time point additional supportive efficacy analysis (to evaluate whether the treatment effect is maintained) and safety analysis (for the purpose of dose(s) selection) will be repeated at the completion of Study Drug treatment.

The treatment portion of the study will be complete when the last enrolled patient reaches 6 months of exposure. All patients will then enter a 16-week post-treatment follow-up period.

Patients  $\geq 18$  and  $\leq 80$  years old with elevated plasma Lp(a) levels ( $\geq 60$  mg/dL ) and a clinical diagnosis of CVD are eligible for enrollment upon meeting the study specific eligibility criteria. Patients will be on standard-of-care preventative therapy for other than elevated Lp(a) CVD risk factors as per current guidelines.

Clinical diagnosis of CVD is defined as documented coronary artery disease (CAD), stroke, or peripheral artery disease (PAD). A diagnosis of CAD has to be documented by any of the following:

- Angiographic evidence of  $\geq 50\%$  stenosis of 1 or more major epicardial coronary arteries
- History of myocardial infarction documented by positive enzymes, and either symptoms of myocardial ischemia, or ECG changes ([Thygesen et al. 2012](#))
- History of coronary revascularization
- Evidence of cardiac ischemia on exercise testing, or imaging study

Patients will be evaluated for study eligibility during Screening, which takes place within 4 weeks prior to Day 1 (the first day of Study Drug administration). Patients who are determined to be eligible, based on screening assessments, will be enrolled in the study at Day 1 and randomly assigned to 1 of the 5 parallel dosing cohorts, with each cohort having a 5:1 ratio to receive ISIS 681257 or matching volume of placebo, respectively, by SC injection for up to 52 weeks.

Following the End-of-Treatment, patients will enter the 16-week post-treatment follow-up period.

### **3.2 Number of Study Centers**

This is a multicenter, multinational study.

### **3.3 Number of Patients**

Approximately 270 patients will be randomized in this study, with approximately 54 patients assigned to each of the 5 treatment cohorts.

### **3.4 Overall Study Duration and Follow-up**

The length of patients' participation in the study may be up to 18 months (72 weeks), which includes a 4-week screening period, an up to 52-week treatment period with Study Drug (ISIS 681257 or placebo), and a 16-week post-treatment follow-up period. The treatment portion of the study will be complete when the last enrolled patient reaches 6 months of exposure.

Patients may be required to attend additional visits for monitoring of AEs or abnormal investigation results. The frequency of additional monitoring will be determined by the Study Medical Monitor in consultation with the Investigator.

#### **3.4.1 Screening**

Patient eligibility for the study will be determined within 4 weeks prior to study.

#### **3.4.2 Treatment**

For each patient minimum treatment duration is 6 months and maximum of 52 weeks.

All patients enrolled will be randomized to a minimum of 6 months of treatment in 1 of 5 treatment cohorts. On completion of the 6 months, patients may continue treatment within the same randomized cohort until the last enrolled patient reaches 6 months of exposure (for continuing safety assessments), with a maximal exposure period of 12 months. When this milestone is met, all patients will then enter a 16-week post-treatment follow-up period.

Eligible patients will report to the Study Center for assessments at specified intervals throughout the 52-week treatment period as detailed in the Schedule of Procedures in [Appendix A](#). During the Treatment, Study Drug (ISIS 681257 or placebo) will be administered by SC injection once weekly, every 2 weeks, or every 4 weeks, depending on cohort assignment.

#### **3.4.3 Post-Treatment**

Patients when completed dosing will enter the 16-week post-treatment follow-up period and will return to the Study Center for 3 follow-up visits 4, 10, and 16 weeks after their last injection of Study Drug as per Appendix A (Follow-up).

The final study visit for each patient will be 16 weeks after the last dose of Study Drug.

### **3.5 End-of-Study**

The End-of-Study is defined as last patient, last visit.

For individual patients, End-of-Study is defined as completion of their last study visit.

### **3.6 Data and Safety Monitoring Board**

An independent Data and Safety Monitoring Board (DSMB) will be assembled to review safety, tolerability and efficacy (as needed) data collected on ISIS 681257 during this study. The DSMB will be constituted to include expertise in medical specialties relevant to the safety of antisense drugs (nephrology, hepatology, hematology and cardiology). Specialist members of the DSMB will be informed and consulted on all treatment-related SAEs relevant to their expertise and all changes of relevant laboratory parameters that trigger stopping rules ([Section 8.6](#)), within 48 hours of receipt of such results. In addition, all accrued safety data relevant to each of medical area specialist will be forwarded monthly for review.

The full DSMB review of all accumulated data will be performed quarterly. Based on its ongoing assessment of the safety and tolerability of ISIS 681257, the DSMB will provide recommendations to the Sponsor for modifying, stopping or continuing the study as planned. Details on the safety assessments, frequency of review, meeting schedules and controlled access to unblinded data are outlined in the DSMB Charter and/or Statistical Analysis Plan (SAP).

## **4. PATIENT ENROLLMENT**

### **4.1 Screening**

Before patients may be enrolled into the study, the Sponsor or designee requires a copy of the Study Center's written independent ethics committee/institutional review board (IEC/IRB) approval of the protocol, informed consent form, and all other patient directed information and/or recruitment material.

Patients or their legally acceptable representatives must sign the consent form before any screening tests or assessments are performed. At the time of consent, the patient will be considered enrolled into the study and will be assigned a unique screening number before any study procedures, including screening procedures, are performed. The screening number and patient identification number must remain constant throughout the entire trial. In the event the patient is re-consented and re-screened the patient must be given a new screening number. Screening numbers and patient identification numbers, once assigned, will not be re-used.

### **4.2 Randomization**

Patients will be randomized after all screening assessments have been completed and after the Investigator has verified that they are eligible per criteria in [Sections 5.1](#) and [5.2](#). No patient may begin treatment prior to randomization and assignment of a unique patient identification number.

Using an Interactive Web-Response System (IXRS), eligible patients will be randomized in a 1:1:1:1:1 ratio to 1 of the 5 parallel-dose cohorts (Cohorts A, B, C, D, or E). Within each dose cohort, patients will be randomized in a 5:1 ratio to receive ISIS 681257 or matching volume of placebo, respectively.

A permuted block schedule will be used. The randomization schedule will be generated and held by an independent vendor.

### 4.3 Replacement of Patients

Patients who withdraw from the study will not be replaced.

### 4.4 Unblinding of Treatment Assignment

The Sponsor and all patients, monitors, and Study Center personnel related to the study will be blinded throughout the study and until all patients have completed the study and the database has been locked. However, if a patient has suffered a SAE (as defined in [Section 9.3.3](#)), and/or when knowledge of the treatment assignment will impact the clinical management of the patient, the Investigator will have the ability to unblind the treatment assignment for that patient using the IXRS. The Sponsor will determine the point at which all treatment assignments will be unblinded. The Sponsor or designee will be informed of the unblinding of a patient within 24 hours. In addition, all SUSARs will be unblinded by the Sponsor's or designee's Drug Safety and Quality Assurance personnel for the purpose of regulatory reporting (see [Section 9.2](#)).

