#### 9.3.3 Serious Adverse Event (SAE)

A SAE is any AE that in the view of either the Investigator or Sponsor, meets any of the following criteria:

- Results in death
- Is life threatening, that is, poses an immediate risk of death at the time of the event
- An AE or suspected adverse reaction is considered “life-threatening” if, in the view of either the Investigator or Sponsor, its occurrence places the patient at immediate risk of death. It does not include an AE or suspected adverse reaction that, had it occurred in a more severe form, might have caused death
- Requires inpatient hospitalization or prolongation of existing hospitalization
- Results in a persistent or significant incapacity or substantial disruption of the ability to conduct normal life functions
- Results in a congenital anomaly or birth defect in the offspring of the patient (whether the patient is male or female)
- Important medical events that may not result in death, are not life-threatening, or do not require hospitalization may also be considered serious when, based upon appropriate medical judgment, they may jeopardize the patient and may require medical or surgical intervention to prevent one of the outcomes listed in this definition. Examples of such medical events include allergic bronchospasm requiring intensive treatment in an emergency room or at home, blood dyscrasias or convulsions that do not result in inpatient hospitalization, or the development of drug dependency or drug abuse

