### **9.4.3 Evaluation of Adverse Events (Serious and Non-Serious)**

The Investigator's opinion of the following should be documented on the Adverse Event Case Report Form:

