#### **9.4.3.1 Relationship to the Study Drug**

The event's relationship to the Study Drug (ISIS 681257 or placebo) is characterized by 1 of the following:

- **Related:** There is clear evidence that the event is related to the use of Study Drug, e.g., confirmation by positive re-challenge test
- **Possible:** The event cannot be explained by the patient's medical condition, concomitant therapy, or other causes, and there is a plausible temporal relationship between the event and Study Drug (ISIS 681257 or placebo) administration
- **Unlikely/Remote:** An event for which an alternative explanation is more likely (e.g., concomitant medications or ongoing medical conditions. For reporting purposes, Unlikely/Remote will be grouped together with Not Related)
- **Not Related:** The event can be readily explained by the patient's underlying medical condition, concomitant therapy, or other causes, and therefore, the Investigator believes no relationship exists between the event and Study Drug

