### **10.1.4 Dose Selection**

Dose selection for the further development will be based on the following efficacy and safety considerations; more than 1 dose may meet these criteria. An effective dose, or dose regimen, will be one that achieves clinically-meaningful reduction in plasma Lp(a) levels. Safety will be evaluated on the basis of incidence of expected and unexpected treatment-related SAEs and other specific safety considerations including the incidence of platelet reductions, and renal or hepatic injury.

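### Section 4.4 lets the investigator break the blind for an SAE alone, and nothing requires causality and severity to be recorded before the code is opened

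*Protocol*

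**What the plan says.** Section 4.4 of the protocol sets blinding of the sponsor, patients, monitors and site staff as the default until all patients have finished and the database is locked. It then makes an exception: "if a patient has suffered a SAE (as defined in [Section 9.3.3](#)), and/or when knowledge of the treatment assignment will impact" the management of the patient, "the Investigator will have the ability to unblind the treatment assignment for that patient using the IXRS". Prior consultation is not mentioned. The control stated is notification afterwards: "The Sponsor or designee will be informed of the unblinding of a patient within 24 hours". Unblinding of SUSARs for regulators is a separate process run by drug-safety and quality-assurance personnel (4.4, 9.2).

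The SAE definition in section 9.3.3 includes an event that "Requires inpatient hospitalization or prolongation of existing hospitalization". Section 9.5.2 takes out prescheduled or elective admissions, subject to documented conditions.

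On attribution, section 9.4.3 states: "The Investigator's opinion of the following should be documented on the Adverse Event Case Report Form". The items that follow include relatedness (9.4.3.1) and severity (9.4.3.2).

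On use, section 10.1.4 states: "Safety will be evaluated on the basis of incidence of expected and unexpected treatment-related SAEs". The same sentence adds platelet reductions and renal or hepatic injury. SAEs considered treatment-related are reported to the DSMB (9.4.1), whose specialist members are consulted within 48 hours (3.6).

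**The concern.** Relatedness is a judgement, and knowing the arm bears directly on it. Under 9.4.3.1 the line that matters lies between Possible and Unlikely/Remote, since the latter is grouped with Not Related for reporting. The line turns on whether the patient's condition, concomitant therapy or another cause explains the event. An investigator who knows the patient is on placebo has a reason to place the event on one side. One who knows the patient is on active drug has a reason to place it on the other. If the code may be opened for an SAE as such, and may be opened before the opinion is recorded, the treatment-related SAE counts can carry a bias that differs by arm. Those counts inform the choice of dose and decide which SAEs go to DSMB specialists within 48 hours. A statistical analysis plan cannot repair this afterwards, because blinding of an attribution cannot be restored once the code is known.

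**Working it through.** The plan states no figure on this point, so there is none to reproduce. The check is of the text, with one calculation for scale.

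**Step 1: what the rule permits.** Let A be that the patient has had an SAE, and B that knowing the assignment will affect the patient's management. The rule in 4.4 is A and/or B.

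| SAE (A) | Matters for care (B) | Allowed under 4.4 | Allowed under B alone |
|---|---|---|---|
| yes | yes | yes | yes |
| no | yes | yes | yes |
| yes | no | yes | no |
| no | no | no | no |

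The SAE condition adds only the third row: an SAE for which the assignment does not matter to care.

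**Step 2: whether the third row serves another stated purpose.** Regulatory reporting is covered by the separate SUSAR route in 4.4 and 9.2, which does not need the investigator to know the arm. No other purpose is stated.

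**Step 3: the order of unblinding and attribution.** Section 9.4.1 requires SAEs to be reported within 24 hours of the site's first knowledge. Sections 9.4.3 to 9.4.3.2 require causality and severity to be documented. None of these, nor 4.4, says that the opinion must be recorded before the code is opened or that it may not be revised afterwards. No blinded adjudication of SAE relatedness is described. The sponsor makes its own relatedness assessment (9.2), but in the setting of SUSAR determination, where it may upgrade and not downgrade. Section 10.1.4 does not say whose attribution counts for dose selection.

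**Step 4: where the attribution goes.** It feeds the treatment-related SAE criterion (10.1.4), the 48-hour specialist DSMB consultation (3.6, 9.4.1), and the summaries of treatment-emergent AEs and SAEs potentially related to Study Drug (10.6.2.1).

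**Step 5: scale.** Section 3.1 gives 225 active and 45 placebo patients; section 10.2 gives 45 active patients per cohort. One SAE whose attribution changes, in a patient with no other treatment-related SAE, moves the rate by:
- one regimen, or pooled placebo: 1/45 = 0.022, or 2.2 percentage points;
- all active regimens pooled: 1/225 = 0.0044, or 0.4 percentage points.

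These are the effects of a single change. They say nothing about how many changes would occur.

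**The case against.** The case against giving this much weight is substantial.

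- **The permission is an ability, not an instruction.** Blinding remains the default. This stands, and it is why no count of code breaks can be given. A reader might multiply an assumed SAE rate by 270 (5% to 20% gives 13.5 to 54) and read the result as needless unblindings. The documents do not support that. They give neither an SAE rate nor a code-break rate, and the product counts patients with an SAE, some of whom may need unblinding for care.
- **Not every admission is an SAE.** Section 9.5.2 removes prescheduled and elective admissions, and section 5.2 excludes patients with recent acute coronary events, stroke, revascularisation or major surgery. A claim that qualifying admissions will be common would be unsupported.
- **Attribution-free evidence is planned.** Section 10.6.2.1 summarises all treatment-emergent SAEs as well as the related ones. A shift in relatedness leaves the first table unchanged. This stands.
- **Most of the safety case is laboratory-based.** The safety sample size rests on platelet counts (10.2), and platelet, renal and hepatic findings rest largely on measured values. A reader might infer that the main safety comparison or the Lp(a) endpoint is compromised; the documents do not support that.
- **Other safeguards exist.** The 24-hour rule makes early recording likely, though it fixes no order. The DSMB specialists receive accrued safety data monthly, and the full DSMB reviews all data quarterly (3.6), so relatedness controls only the rapid consultation.
- **Wider harms are not shown.** A reader might infer that the patient's own reporting or background treatment would change. Section 4.4 gives access to the investigator and does not say the patient is told, and section 8.10.1 requires stable lipid-lowering and antiplatelet regimens. Nor can it be said that an investigator who knows the arm is placebo will always record no relationship.

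None of this supplies a reason for the SAE-alone condition or fixes the order of attribution and unblinding. Prompts or flags may sit in IXRS specifications that are not shown, but the permission itself is a protocol rule.

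**Conclusion.** The point holds in a limited form. Section 4.4 as worded allows an investigator to open the code for an SAE when care does not require it, and the protocol does not require causality and severity to be recorded first. Some of the attributions behind one stated dose-selection input, and behind the rapid DSMB consultation, could therefore be made unblinded. The sensitivity is 2.2 points per re-attributed SAE in a group of 45. The number of such events cannot be estimated from the documents. The conclusion assumes that and/or is read in its ordinary sense and that no rule outside the protocol restricts the permission. It does not extend to efficacy, to the laboratory-based safety criteria or to the all-SAE summary. This is a worthwhile and inexpensive tightening of a stated rule, not a defect that puts the trial's main comparisons in doubt.

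**What to change.** In section 4.4, remove the SAE-alone condition so that investigator unblinding rests on the condition already there: that knowledge of the assignment will impact the patient's clinical management. An SAE that meets this condition still qualifies. Add one requirement, in 4.4 or 9.4.3, that causality and severity be entered before the code is opened unless urgency prevents it. An IXRS prompt can enforce the order.

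The cost is a short change of wording and one extra data-entry step before a non-urgent code break. Access needed for care and the separate SUSAR route are unchanged.

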## 5. PATIENT ELIGIBILITY

To be eligible to participate in this study candidates must meet the following eligibility criteria at within 4 weeks of Study Day 1 or at the time point specified in the individual eligibility criterion listed.

### 5.1 Inclusion Criteria

1. Must have given written informed consent (signed and dated) and any authorizations required by local law and be able to comply with all study requirements
2. Males or females aged  $\geq 18$  and  $\leq 80$  years old at the time of informed consent
3. Clinical diagnosis of CVD defined as documented coronary artery disease (CAD), stroke, or peripheral artery disease
4. Lp(a) plasma level  $\geq 60$  mg/dL
5. Must be on standard-of-care preventative therapy for other than elevated Lp(a) CVD risk factors
6. Patients on the following medications must be on a stable regimen for at least 4 weeks prior to Screening and expected to remain on a stable regimen through the end of the post-treatment follow-up period:
  - a. lipid lowering drugs (statins, ezetimibe, proprotein convertase subtilisin/kexin type 9 [PCSK9s] inhibitors, niacin, fibrates, fish oil or other products containing omega-3 fatty acids including OTC preparations)
  - b. antiplatelet drugs
  - c. testosterone, estrogens, progesterone, growth hormone or progestins

7. Females: must be non-pregnant and non-lactating and either:
  - a. surgically sterile (e.g., tubal occlusion, hysterectomy, bilateral salpingectomy, bilateral oophorectomy)
  - b. post-menopausal (defined as 12 months of spontaneous amenorrhea in females > 55 years of age or, in females ≤ 55 years, 12 months of spontaneous amenorrhea without an alternative medical cause and FSH levels in the postmenopausal range for the laboratory involved)
  - c. Abstinent\* or
  - d. if engaged in sexual relations of child-bearing potential, agree to use 2 highly effective contraceptive methods (refer to [Section 6.3.1](#)) from the time of signing the informed consent form until at least 16 weeks after the last dose of Study Drug (ISIS 681257 or placebo)

\* Abstinence is only acceptable as true abstinence, i.e., when this is in line with the preferred and usual lifestyle of the patient. Periodic abstinence (e.g., calendar, ovulation, symptothermal, post-ovulation methods), declaration of abstinence for the duration of a trial and withdrawal are not acceptable methods of contraception
8. Males must be surgically sterile or, if engaged in sexual relations with a female of child-bearing potential, the patient must be using an acceptable contraceptive method (refer to [Section 6.3.1](#)) from the time of signing the informed consent form until at least 16 weeks after the last dose of ISIS 681257

